When nodal disease is included in the sum of target lesions and the nodes decrease to 'normal' size (<10 mm), they may still have a measurement reported on scans. This measurement should be recorded even though the nodes are normal in order not to overstate progression should it be based on increase in size of the nodes. As noted earlier, this means that patients with irCR may not have a total sum of 'zero' on the case report form (CRF).

Patients with a global deterioration of health status requiring discontinuation of treatment without objective evidence of disease progression at that time should be reported as 'symptomatic deterioration'. Every effort should be made to document objective progression even after discontinuation of treatment. Symptomatic deterioration is *not* a descriptor of an objective response: it is a reason for stopping study therapy. The objective response status of such patients is to be determined by evaluation of target and non-target disease as shown in [Table 1](#).

CONFIRMATION/DURATION OF RESPONSE

Confirmation

Objective responses should be confirmed by CT and/or MRI scans obtained no less than 4 weeks after the original scan.

Duration of overall response

The duration of overall response is measure from the time measurement criteria are first met for irCR/irPR (whichever is first recorded) until the first date that recurrent or progressive disease is objectively documented (taking as reference for progressive disease the smallest measurements recorded on study). The duration of overall complete response is measured from the time measurement criteria are first met for irCR until the first date that recurrent disease is objectively documented.

Duration of stable disease

Stable disease is measured from the start of the treatment until the criteria for progression are met, taking as reference the *smallest sum on study* (if the baseline sum is the smallest, this is the reference for calculation of irPD).

## LIST OF ABBREVIATIONS

ADA	Anti-drug antibody
AE	Adverse event
AESI	Adverse event of special interest
CI	Confidence interval
CR	Complete response
CTCAE	Common Terminology Criteria for Adverse Events
DLT	Dose limiting toxicity
DoR	Duration of response
ECG	Electrocardiogram
eCRF	Electronic case report form
GEJ	Gastroesophageal Junction
irCR	immune-related complete response
IRE	Immediately reportable events
irPD	immune-related progressive disease
irPR	immune-related partial response
irRECIST	immune-related Response Evaluation Criteria in Solid Tumors
irSD	immune-related stable disease
IV	Intravenously
LVEF	Left ventricular ejection fraction
MAD	Maximum administrated dose
MedDRA	Medical dictionary for regulatory activities
MTD	Maximum tolerated dose
MUGA	Multi Gated Acquisition Scan

ORR	Objective response rate
OS	Overall survival
PD	Progressive disease
PD	pharmacodynamics
PD-L1	Programmed death-ligand 1
PFS	Progression-free survival
PK	Pharmacokinetics
PT	Preferred Term
PR	Partial response
RECIST	Response Evaluation Criteria in Solid Tumors
SAE	Serious adverse event
SAP	Statistical analysis plan
SAS	Statistical Analysis System
SD	Stable disease
SOC	System Organ Class
SPP	Statistical programming plan
TEAE	Treatment emergent adverse event
TLF	Table, listing and figure

## **1 INTRODUCTION**

This study is an open-label, dose escalation, Phase 1b/2 study designed to characterize the safety, tolerability, pharmacokinetics (PK), pharmacodynamics (PD), immunogenicity, and preliminary antitumor activity of margetuximab administered intravenously (IV) once every 3 weeks in combination with 200 mg pembrolizumab administered IV once every 3 weeks in patients with relapsed/refractory unresectable locally advanced or metastatic HER2+ gastroesophageal junction (GEJ) or gastric cancer (GC).

This SAP describes in detail the statistical methods to be used for analysis of the primary and secondary efficacy endpoints, the safety endpoints, and the PK parameters to be collected from this study.

## **2 STUDY OBJECTIVES**

### **2.1 Primary Objective(s)**

The primary objectives of this study are:

- To characterize the safety, tolerability, dose-limiting toxicities (DLT), and maximum tolerated dose (MTD) or maximum administered dose (MAD) (if no MTD is defined) of margetuximab when administered IV every 3 weeks in combination with 200 mg pembrolizumab administered IV every 3 weeks to patients with relapsed/refractory advanced HER2+ GEJ or GC.
- To investigate the preliminary anti-tumor activity, as measured by objective response rate (ORR) and response duration, of margetuximab administered IV every 3 weeks in combination with pembrolizumab administered IV every 3 weeks using both conventional Response Evaluation Criteria in Solid Tumors (RECIST) 1.1 and immune-related RECIST (irRECIST), in patients that have failed first-line trastuzumab-containing regimens.

### **2.2 Secondary Objective(s)**

Secondary objectives of this study are:

- To investigate the preliminary effect on overall survival (OS) and progression-free survival (PFS) of margetuximab administered IV every 3 weeks in combination with pembrolizumab administered IV every 3 weeks.
- To characterize the PD activity of margetuximab administered IV every 3 weeks in combination with pembrolizumab administered IV every 3 weeks.
- To characterize the PK and immunogenicity of margetuximab administered IV every 3 weeks in combination with pembrolizumab administered IV every 3 weeks.

### **3 STUDY DESIGN AND PLAN**

#### **3.1 Overall Study Design and Plan**

This study is a Phase 1b/2, open-label, dose escalation and cohort expansion study designed to characterize the safety, tolerability, PK, PD, immunogenicity, and preliminary antitumor activity of margetuximab administered IV every 3 weeks in combination with pembrolizumab administered IV every 3 weeks in patients with relapsed/refractory unresectable locally advanced or metastatic HER2+ GEJ or gastric cancer.

The study consists of a Dose Escalation Phase to determine the MTD or MAD (if no MTD is defined) of escalating doses of margetuximab administered in combination with a fixed dose of 200 mg pembrolizumab, followed by a Cohort Expansion Phase to further define the safety and initial efficacy of the combination with the margetuximab dose established in the first phase.

Both margetuximab and pembrolizumab will be administered once every 3 weeks. Both agents will be administered on the same day, with pembrolizumab administered first, followed by margetuximab. Each cycle of therapy is defined as 3 weeks, in which margetuximab and pembrolizumab will be given on Day 1. Tumor assessments will be performed every 6 weeks (i.e., following 2 cycles of treatment [prior to dosing for Cycles 3, 5, 7, etc.]) for the first 24 weeks on treatment; thereafter, tumor assessments will be performed every 12 weeks until documented progression, initiation of alternative anti-cancer therapy, lost to follow up, withdrawal of informed consent, death, or end of study.

Assuming the patient remains clinically stable, has not experienced immune-related progressive disease (irPD), and does not experience unacceptable toxicity that necessitates permanent discontinuation of both study drugs, treatment with the combination may continue for up to 2 years. Following up to 2 years of combination treatment, therapy will be discontinued, and patients will be followed in Efficacy Follow-up Period.

See the Study Evaluation Table of the latest version of the protocol for the full description of study evaluations, including the number and timing of visits and the procedures to be performed at each visit.

#### **3.2 Sample Size**

The number of patients enrolled in the Dose Escalation Phase (Part A) cannot be precisely determined in advance and could range up to 12 patients based on 3+3 design applied to 2 dose levels. This patient number does not take into account patient replacement for non-evaluable patients.

The Cohort Expansion Phases of the trial will enroll up to 85 patients.

The first expansion cohort (Part B) includes 30 patients in North America and 30 patients in Asia with relapsed/refractory unresectable locally advanced or metastatic HER2+ GEJ or GC.

Part C will enroll up to 25 patients in North American and/or Asia with relapsed/refractory unresectable locally advanced or metastatic HER2+ (IHC 3+) gene amplification GC.

The sample size for each part in the Cohort Expansion Phase is primarily based on providing preliminary estimation of responses. The following table (**Table 1**) provides the 2-sided 95% confidence interval (CI) for a number of potential response rates under various sample sizes.

**Table 1 Response Rates and 95% Confidence Intervals**

Sample Size	Number of Responses	Response Rate (%)	95% Confidence Interval (%)
30	1	3.3	0 – 17
30	5	16.7	5.6 – 34.7
30	10	33.3	17.3 – 52.8
30	15	50.0	31.3- 68.7
30	20	66.7	47.2 – 82.7
25	1	4	0 – 20.4
25	3	12	2.5 – 31.2
25	6	24	9.4 – 45.1
25	9	36	18.0 – 57.5

After 15 patients were enrolled in each region in Part B and after each patient had at least one post-baseline tumor assessment, a futility rule was applied and enrollment in that region was continued. The enrollment could have been stopped if there was no more than one response. One response out of 15 patients will have greater than 80% confidence to rule out the response rate of 20% or higher (the upper limit of one-sided 80% CI for response rate < 20%).

## 4 ANALYSIS POPULATIONS

Two populations will be used for analysis, the **Safety Population** and the **Response Evaluable Population**, as defined below:

- **Safety Population:** All patients who received at least one dose of either margetuximab or pembrolizumab. This population will be used for safety analysis and for analysis of PFS and OS. Patients who receive at least one dose of margetuximab will be included in PK, PD, and immunogenicity analyses.
- **Response Evaluable Population:** All patients who have baseline measurable disease and received one dose of either margetuximab or pembrolizumab. This population will be used for analysis of ORR.

Patients who withdraw before receiving all protocol-specified treatment before completion of the DLT evaluation period for a reason unrelated to drug toxicity will be considered to have inadequate data to support dose escalation. In this case, replacement patients may be enrolled at the same dose level and schedule as necessary to complete the cohort.

## 5 ENDPOINTS

### 5.1 Efficacy Endpoints

#### 5.1.1 Response Endpoints

- Response by RECIST v1.1: The response by radiographic assessment using RECIST v1.1 is categorized as complete response (CR), partial response (PR), stable disease (SD), and progressive disease (PD). The CR and PR are required to be confirmed at least 28 days after the initial observation of such response.
- Immune-related Response by irRECIST: The immune-related response by radiographic assessment using irRECIST is categorized as immune-related complete response (irCR), immune-related partial response (irPR), immune-related stable disease (irSD), and immune-related progressive disease (irPD). The irCR, irPR and irPD are required to be confirmed at least 28 days after the initial observation of such response.

#### 5.1.2 Time to Event Endpoints

- Progression-free survival (PFS): The PFS is defined as the time from the first dose date to the date of first documented progression or death from any cause, whichever occurs first. For patients who are not known to be dead or progressed at the time of data cut-off for PFS analysis, the PFS will be censored at the date of the last tumor assessment. The documented progression is determined by radiographic assessment using RECIST v1.1. PFS will be calculated as:

$$\text{PFS (months)} = (\text{date of event [documented progression or death] or date of censoring} - \text{first dose date} + 1) / (365.25/12)$$

- Duration of response (DoR): The DoR is defined as the time from the date of initial response to the date of first documented progression or death from any cause, whichever occurs first. DoR will be analyzed for responding patients only. For responding patients who are not known to be dead or progressed at the time of data cut-off for DoR analysis, the DoR will be censored at the date of the last tumor assessment. The documented progression is determined by radiographic assessment using RECIST v1.1. DoR will be calculated as:

$$\text{DoR(months)} = (\text{date of event [documented progression or death] or date of censoring} - \text{date of initial response} + 1) / (365.25/12)$$

DoR may also be determined by irRECIST.

- Overall survival (OS): The OS is defined as the time from the first dose date to the date of death from any cause. For patients who are not known to be dead at the time of data cut-off for OS analysis, the OS will be censored at the time they are last known to be alive. OS will be calculated as:

$$\text{OS (months)} = (\text{date of death or last known alive} - \text{first dose date} + 1) / (365.25/12)$$

## **5.2 Safety Endpoints**

### **5.2.1 Adverse Events**

Safety will primarily be addressed by evaluations of adverse events (AEs). An AE is defined as any untoward medical occurrence in a patient or clinical investigation subject, occurring as part of a research study, which does not necessarily have to have a causal relationship with use of a medicinal product. An AE can therefore be any unfavorable and unintended sign (including an abnormal laboratory finding, for example), symptom, or disease whether or not considered related to the medicinal product.

AEs will be captured starting with signing of the informed consent form through 28 days following cessation of treatment. Only treatment-related serious AEs will be captured afterwards. These events will be recorded by the Investigators in the eCRFs. Verbatim terms will be coded to lower-level terms using the most recent version of the Medical Dictionary for Regulatory Activities (MedDRA).

Only treatment-emergent adverse events (TEAEs) will be summarized as safety endpoints. A TEAE is defined as any event that is newly occurring on or after the administration of study drug or an event that existed before but increased in severity on or after study drug administration. For each TEAE, a new AE is recorded whenever the toxicity/severity changes. AEs that occurred before and did not worsen on or after study drug administration are considered non-treatment emergent AEs and will only be summarized as medical history.

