7.2 Medical History

A complete medical history should be obtained during the screening visit. All concurrent medical conditions in the last 60 days and any significant medical conditions (e.g., hospitalizations, surgeries, prior cancer history) should be collected. During the screening period (prior to first dose of pembrolizumab or margetuximab), any untoward event that occurs should be recorded as medical history and not as an AE, unless it is due to a protocol-related procedure. Thereafter (i.e., after the time of study drug administration), any untoward event should be collected as an AE.

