7.9.2 Adverse Event: Definitions

7.9.2.1 Adverse Event

Progression of the cancer under study is not considered an adverse event unless it is considered to be drug-related by the investigator.

An adverse event is any untoward medical occurrence in a patient or clinical investigation patient administered a pharmaceutical product and which does not necessarily have to have a causal relationship with this treatment. An AE can therefore be any unfavorable and unintended sign (e.g., an abnormal laboratory finding), symptom, or disease temporally associated with the use of a medicinal product, whether or not considered related to the medicinal product.

An adverse event will also be considered to be any untoward effect of a study-related procedure, which is conducted after signed informed consent and prior to study drug administration.

All adverse events will be recorded from the time the consent form is signed through 28 days following cessation of treatment and at each examination on the Adverse Event case report forms/worksheets. The reporting timeframe for adverse events meeting any serious criteria is described in [Section 7.9.6](#) - Notification to the Sponsor of Events Requiring Immediate Reporting.

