9.4 Safety Endpoint(s)

9.4.1 Adverse Events

Adverse events will be coded to the Medical Dictionary for Regulatory Activities (MedDRA) dictionary. Only treatment-emergent AEs, as defined in [Section 7.9.2](#), will be summarized in tables. Events prior to treatment (e.g., due to study-related procedure) will be listed in an appendix to the final study report.

The following tables of adverse event data will be created to summarize the number and percent of patients who experience at least one event of each of the following types:

- Any TEAEs
- Treatment related TEAEs
- TEAEs with CTCAE Grade severity Grade ≥ 3
- Treatment related TEAEs by CTCAE Grade severity Grade ≥ 3
- TEAEs related to each individual study drug
- Any SAEs (this may be a listing if there are few events)
- Treatment related SAEs
- SAEs related to each individual study drug
- Fatal AEs (this may be a listing if there are few events)
- AESIs
- IREs
- TEAEs that result in study discontinuation
- TEAEs which lead to interruption of each individual study drug
- TEAEs that lead to withdrawal of each individual study drug

All of these tables will display the number and percent of patients that experience the given event and will display events by MedDRA System Organ Class (SOC) and Preferred Term. Events will be displayed alphabetically for SOC and Preferred Term. An overall summary of AEs will display the number and percent of patient/patients who experience at least one event of each of the above AE types.

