## **6.7 Safety Endpoint Analyses**

### **6.7.1 Treatment Emergent Adverse Events**

Only TEAEs will be summarized. The non-treatment emergent AEs are included in medical history summaries. Note that all TEAEs recorded in the eCRFs will be included in the safety analysis, even if they are outside the collection window.

The following TEAEs will be provided in summary tables as well as displayed in listings:

- Any TEAEs
- Treatment-related TEAEs
- TEAEs by CTCAE severity Grade  $\geq 3$
- Treatment-related TEAEs with CTCAE severity Grade  $\geq 3$
- TEAEs related to each individual study drug
- Any SAEs
- Treatment-related SAEs
- SAEs related to each individual drug
- Fatal AEs
- AESIs
- IREs
- TEAEs that result in study discontinuation
- TEAEs that lead to interruption of each individual drug
- TEAEs that lead to withdrawal of each individual study drug

All of these summaries will display the number and percent of patients who experience the given event and will display events by System/Organ/Class (SOC) and Preferred Term (PT). Events will be displayed alphabetically for SOC and in descending order of overall PT incidence within each SOC.

In addition, an overall summary table will be generated to display the number and percent of patients who experience at least one event of each of above TEAE types.

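### The SAP sends pre-dose adverse events caused by study procedures to medical history, although the protocol classes them as adverse events and promises to list them

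*SAP*

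**What the plan says.** **SAP.** Capture starts at consent: "AEs will be captured starting with signing of the informed consent form through 28 days following cessation of treatment" (section 5.2.1). The same section then says that AEs present before dosing that did not worsen "are considered non-treatment emergent AEs and will only be summarized as medical history". Section 6.7.1 applies this to the analysis: "Only TEAEs will be summarized. The non-treatment emergent AEs are included in medical history summaries". The outputs are introduced by "The following TEAEs will be provided in summary tables as well as displayed in listings", and the SAE categories stand under that sentence. Neither section mentions study procedures.

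**Protocol.** Section 7.9.2.1 extends the AE definition to the period before dosing: "An adverse event will also be considered to be any untoward effect of a study-related procedure, which is conducted after signed informed consent", as long as it precedes study drug. Section 7.2 says that an untoward event during screening "should be recorded as medical history and not as an AE, unless it is due to a protocol-related procedure". Section 7.9.1 makes the same exception and collects protocol-related AEs and SAEs from consent. Section 7.9.5 puts a procedure-related pre-dose event on the eCRF as an AE. On reporting, section 9.4.1 limits the tables to treatment-emergent events but adds: "Events prior to treatment (e.g., due to study-related procedure) will be listed in an appendix to the final study report".

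**The concern.** The two documents treat the same event differently. The protocol separates pre-dose events into those caused by a study procedure (AEs) and the rest (medical history). The SAP makes no such separation and uses the word only, which leaves no evident room for the protocol's appendix listing.

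The rule falls on the very events the protocol exempts. If sites follow protocol 7.2 and 7.9.5, other pre-dose events are entered as medical history from the start, so the pre-dose entries on the AE form should be mainly the procedure-related ones. The SAP would move these into medical history at the analysis stage.

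What is at stake is the visibility of harm from taking part in the trial. A complication of a research biopsy is not pre-existing history. Shown as such, it is misclassified in the report and adds an event to the baseline table that does not belong there.

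**Working it through.** The plan gives no figure for this point, so the check compares the rules case by case.

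| Event | Protocol | SAP | Agree? |
|---|---|---|---|
| Pre-dose, not caused by a procedure, does not worsen | Medical history (7.2, 7.9.1, 7.9.5) | Medical history (5.2.1, 6.7.1) | Yes, though protocol 9.4.1 speaks of pre-treatment events in general |
| Pre-dose, caused by a procedure, does not worsen | AE on the eCRF (7.9.2.1, 7.9.5); not tabulated; listed in an appendix (9.4.1) | Medical history summary only; no AE or SAE table or listing specified | **No** |
| Pre-dose, any cause, worsens after dosing | Treatment-emergent (7.9.2.4) | Treatment-emergent (5.2.1) | Yes |
| Complication of the Cycle 2 Day 1 biopsy | Treatment-emergent | Treatment-emergent | Yes |
| Caused by a procedure, patient never dosed | AE; the 9.4.1 listing sets no dosing condition | Outside the Safety Population (section 4); counted as never treated, with a reason if collected (6.3.1) | **No** |

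The conflict is therefore confined to procedure-related events before the first dose that do not later worsen, including those in patients who never start treatment.

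**Seriousness.** The SAP's SAE categories sit under the sentence restricting outputs to treatment-emergent events. A serious pre-dose procedure complication therefore reaches no AE or SAE output specified in section 6.7.1. The note there admitting events outside the collection window does not help, because it too applies only to treatment-emergent events.

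**Exposure.**
- Protocol 7.7.1.2 requires consent to a baseline research biopsy from at least 20 of the 60 Part B patients.
- Part C requires none, and the Part A schedule (Appendix 1) lists only an archival specimen.
- Section 7.7.1.2 places the biopsy within 7 days before dosing, and Appendix 2 (footnote 20) within 3 days. These passages must be reconciled, but both put it before the first dose.

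**Size.** The documents give no complication rate. Assuming 2% to 10% purely to show scale, expected events = biopsies × rate:
- 20 × 0.02 = 0.4
- 20 × 0.10 = 2
- 60 × 0.10 = 6, which supposes that every Part B patient has a biopsy, a ceiling and not the plan

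**The case against.** The strongest reply is that little is lost. The protocol also keeps these events out of every AE table, so the documents differ by one appendix listing and a label. The events are still captured from consent, SAEs still go to the sponsor within 24 hours, and the SAP still shows the events under medical history. The SAP describes how events are summarized and may simply be silent about the listing. The full list of outputs sits in a separate statistical programming plan (SAP section 7), which is not among the documents.

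Most of this stands, and it rules out three stronger readings that a reader might infer:

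- *That the SAP contradicts the protocol on all pre-dose events.* It does not. Without a procedural cause, both documents use medical history.
- *That these events vanish from the safety report, or that the primary safety objective is biased.* The documents do not support this. The objective concerns the drug combination, DLTs are counted only after the first pembrolizumab dose, and no treatment-emergent rate changes.
- *That the SAP singles out biopsies, or that no listing will exist.* The SAP never mentions biopsies; they are caught because the exception is missing. What the programming plan contains is unknown.

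Silence does not fully answer the point, however. SAP 5.2.1 does more than omit a listing: it reclassifies the events, against protocol 7.2 and 7.9.2.1. SAP section 7 describes the programming plan's outputs as based on the analyses in the SAP, so that plan cannot be presumed to restore a listing the SAP does not describe.

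**Conclusion.** The concern holds in a narrow form. For AEs and SAEs caused by a study procedure between consent and first dose that do not worsen after dosing, the SAP gives a classification the protocol rejects and specifies none of the listing the protocol promises. This is a stated rule with a wrong result, not merely missing detail, and it should be corrected.

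The consequence is limited to how these events are classified and whether they are listed. Their number is likely small, possibly zero, and cannot be derived from the documents. The conclusion does not rest on the assumed complication rate. It rests on reading the SAP as written and on the programming plan not adding the listing independently.

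**What to change.** In SAP 5.2.1 and 6.7.1, exempt from the medical-history rule any AE or SAE between consent and first dose that is attributed to a protocol procedure. Add the separate pre-treatment AE/SAE listing that protocol 9.4.1 requires, and state that it covers all consented patients, including those never dosed, since the Safety Population would leave the latter out. Pre-dose events without a procedural cause can stay in medical history.

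The cost is about two sentences and one listing. Protocol 7.9.5 already puts the data on the eCRF, and no efficacy analysis or treatment-emergent count is touched. A tabulation by procedure is not needed to meet the protocol, which asks only for a listing.
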